Does Contrast-Enhanced
Ultrasound Positively Influence
Selection of Biopsy Sites when
Evaluating Transplant Kidneys?

NCT02625428

26 November 2014

Does Contrast-Enhanced Ultrasound Positively Influence Selection of Biopsy Sites when Evaluating Transplant Kidneys?

Protocol Date: 26 November 2014

[name], MD¹, Co-principal Investigator
[name], MD¹, Co-principal Investigator
[name], MD²
[name], MD³
[name], MD¹
[name], MD¹
[name]⁴

Introduction

Histopathological changes in kidney allograft are not always homogeneous. [1] Common pathologic abnormalities found on biopsy of transplanted organs, including renal transplants, can be patchy in distribution, especially in rejection and chronic nephropathy. [2-6] This may result in a suboptimal sample when performing a random transplant renal biopsy. [4, 6] Strategies to minimize sampling error include using larger needles or obtaining additional cores, since complications of biopsy remain very low and the benefit far exceeds the risk. [4, 6, 7] We hypothesize that contrast-enhanced ultrasound (CEUS) may help evaluate segmental differences in renal perfusion better than Doppler Ultrasound and thus help direct the biopsy to the most abnormal part of the renal cortex. This should maximize detection and increase the odds of demonstrating the true grade/severity of the histopathological abnormality.

CEUS has been FDA approved for echocardiography but its use elsewhere in the body is considered off-label. It has been used extensively outside the United States within the abdomen, but most commonly for liver masses. CEUS investigations within transplant kidneys have shown additional information can be obtained when compared to gray-scale and Doppler ultrasound. Apart from a better estimate of parenchymal perfusion it allows for evaluation of graft vascular kinetics, including quantitative measurements, e.g. time-to-peak enhancement (TTP) within the cortex or pyramids. [8-14] Studies have also shown CEUS is more sensitive to renal perfusion defects than Tc-DTPA. [15] This ability of CEUS to evaluate perfusion over time may help target renal transplant biopsies to the most abnormal segments.

Hypothesis/Expected Results

CEUS targeted biopsies to areas of decreased or inhomogeneous perfusion will show disease processes significantly more often or of a higher severity than (non-targeted) random biopsies. Additionally, this directed biopsy may demonstrate more significant or advanced disease, as measured by Banff criteria, when compared to a routine non-targeted biopsy. Random biopsies

of different segments in the same kidney, when no focal or segmental CEUS abnormality is demonstrated, will not be significantly discordant for disease or Banff criteria.

Proposed investigation

IRB approval from our institution will be obtained for this pilot study of 40 consecutive consenting male and female adult patients over 18 years of age undergoing renal transplant ultrasound-guided percutaneous biopsy within 24 months post-transplant, including patients undergoing biopsy to evaluate a recent rise in serum creatinine, so-called for cause biopsies and patients undergoing routine protocol (surveillance) biopsies without other evidence of renal dysfunction. Pregnant patients will be excluded. The routine protocol biopsies are done at 4 months and 1 year after transplant mostly looking for subclinical rejection. Informed written consent (IRB approved consent form) will be obtained from all patients prior to the scan and biopsy procedure. This will include consent for the off-label use of Optison and the need to obtain 2 or 3 biopsies specimens, when routinely only 1 or 2 are obtained. All patients will meet our standard anticoagulation guidelines for undergoing renal transplant biopsy.

CEUS will be performed in addition to our routine color-Doppler ultrasound evaluation of the transplant kidney prior to the biopsy. One vial (3.0 mL) of Optison will be utilized for each patient, with expected doses to be in the range of 1-1.5 mL for each scan sequence, allowing up to 2 to 3 scan sequences per patient exam. Low mechanical index settings and coded harmonics will be utilized. Each scan sequence will be recorded for up to 5 minutes. Post-processing will be performed using an off-line workstation if needed.

All patients will have at least 2 core biopsies of their transplant kidney under ultrasound guidance, using the cortical tangential approach whenever possible. [7] One core will be obtained from the most easily accessible location, usually the upper pole, without consideration of CEUS results (labeled “random #”, with “#” the ordinal number of the biopsy). A second core biopsy will be obtained from a segment that demonstrates variable CEUS perfusion. This sample will be labeled “targeted #”. If no abnormality is detected with CEUS, a second biopsy will still be performed in a distinctly separate location from the first (labeled “random #”). Conceivably, there could be additional biopsies added to the same “targeted #” or “random #” container if the previous biopsy in that region is/are not satisfactory or inadequate for any reason and obtained from the same general region of the kidney. We will be targeting areas of low perfusion. Many studies have shown CEUS using “global” cortical perfusion analysis can significantly aid detection of rejection (and other processes, e.g. chronic allograft nephropathy). [8, 9, 12, 14, 16] In pigs, CEUS is very good at detecting focal perfusion abnormalities. [15, 17] CEUS is better at evaluating the cortical perfusion, and not limited to segmental and interlobar artery evaluations, as with standard color-Doppler evaluations. Areas of no perfusion representing cortical infarcts would not contribute to the diagnosis and will not be targeted. The perfusion characteristics of each site based on CEUS findings will be recorded. Each will also be categorized as “For Cause” or “Surveillance”.

The order in which the randomized and targeted biopsies are performed will be randomized. Biopsies specimens sent for analysis will be labeled in order only as #1 and #2, blinded to the pathologists, with the full description (including “targeted” or “random” with the #) recorded by the performing radiologist prospectively. Each biopsy core will be evaluated separately by the pathologists. Pathologists will be as definitive as possible in making a diagnosis and specifying Banff scores for each individual biopsy core. Differences in pathology will then be reviewed and recorded as to presence of disease and differences in Banff scores.

Safety and Adverse Events

It is standard practice that patients be kept for observation 1 hour post biopsy and called by the nurse at 24 hours. Those patients participating in the study will also be called 72 hours post procedure. Any complications or adverse effects occurring within 1 week of the procedure will be recorded.

When an adverse event has been identified, the study team will take appropriate action necessary to protect the study participant and then complete the Study Adverse event Worksheet and log. The investigator will evaluate the event and determine the necessary follow-up and reporting required.

The investigator will report to the Mayo IRB any UPIRTSOs and Non-UPIRTSOs according to the Mayo IRB Policy and Procedures.

Data Handling and Statistical Analysis

All data will be entered into a secure database and anonymized. The statistician will create REDCap electronic data forms. Statistical analysis will be performed by our statistician after data has been obtained for all 40 patients. Detection rates would be compared by using the McNemar test. Based on our last 50 renal transplant biopsies, 84% were “surveillance” and 16% were “For Cause”. Positive rejection rates have been reported at 12-61% (1 month survey at MCA = 16% rejection) for the surveillance group [18-20] and 25-46% (1 month survey at MCA= 25% rejection) for the For Cause group. [20, 21] Using 12% and 25% as the baseline rate of rejection detected for Protocol and For Cause biopsies, respectively, we expect 17% of random biopsies to be positive for rejection ($0.25 \times 0.16 + 0.16 \times 0.84 = 0.17$). Conservatively, assuming a 10% false negative rate by CEUS biopsy, a sample of 40 patients has 80% power (alpha .05) if detection increases by 20 percentage points from 17% to 37%.

Ethical Considerations

This study is to be conducted according to United States government regulations and Institutional research policies and procedures. The investigator will ensure that the basic principles of “Good Clinical Practice,” as outlined in Title 21 of Code of Federal Regulations (CFR), Part 50, “Protection of Human Subjects”; 21 CFR, part 54, “Financial Disclosure by Clinical Investigators”; 21 CFR, part 56, “Institutional Review Boards”; and 21 CFR, Part 11, “Electronic Records, Electronic Signature,” are adhered to.

This protocol and any amendments will be submitted to a properly constituted local Institutional Review Board (IRB), in agreement with local legal prescriptions, for formal approval of the study. The decision of the IRB concerning the conduct of the study will be made in writing to the investigator before commencement of this study.

All subjects for this study will be provided a consent form describing this study and providing sufficient information for subjects to make an informed decision about their participation in this study. This consent form will be submitted with the protocol for review and approval by the IRB for the study. The formal consent of a subject, using the approved IRB consent form, must be obtained before that subject undergoes any study procedure. The consent form must be signed by the subject and the individual obtaining consent.

Expected Deliverables

Expected time-frame, once funded, for patient recruitment and completion of procedures is 6 months, and for all deliverables is 1 year. At least 1 scientific paper or poster will be submitted for presentation at a major radiology meeting (e.g. RSNA, ARRS, or SIR annual meetings) and we will submit a paper for publication in a radiology or medical journal (e.g. Radiology, AJR, or JVIR.) All (anonymized) data will be sent to GE. Depending on results, this may serve as a nidus for a larger study.

Support Requested from GE

Provide forty vials of ultrasound contrast media (Optison). Provide post-processing quantification software for CEUS ultrasound data. Additional pathology costs, due to one additional sample for each of the 40 patients. Ten days (approximately 4% FTE) of paid radiologist “Categorical” research time. 10 hours of technologist time. Cost of statistical analysis. IRB and other fees.

¹Department of Radiology, Ultrasound Section; ²Department of Pathology; ³Department of Nephrology; ⁴Department of Biostatistics; Mayo Clinic Arizona

References

1. Piovesan, A.C., et al., *Multifocal Renal Allograft Biopsy: Impact on Therapeutic Decisions*. Transplantation Proceedings, 2008. **40**(10): p. 3397-3400.
2. Sharples, L.D., et al., *Error rates with which endomyocardial biopsy specimens are graded for rejection after cardiac transplantation*. American Journal of Cardiology, 1992. **70**(4): p. 527-30.
3. Yamataka, A., et al., *Patchy distribution of rejection changes in small intestinal transplantation*. Journal of Pediatric Surgery, 1992. **27**(5): p. 602-3.

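### A non-significant test cannot show that random cores from CEUS-normal kidneys agree, and McNemar, the only test named, does not measure how often they disagree

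*Combined protocol and SAP*

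**What the plan says.** The last sentence under Hypothesis/Expected Results concerns kidneys in which CEUS shows nothing to target. It predicts that random cores from different segments, "when no focal or segmental CEUS abnormality is demonstrated, will not be significantly discordant for disease or Banff criteria".

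Proposed investigation describes how such pairs arise. The first core is taken as follows: "One core will be obtained from the most easily accessible location, usually the upper pole, without consideration of CEUS results". When CEUS is normal, a second core is still taken, from a clearly different place. The cores are read separately, and then "Differences in pathology will then be reviewed and recorded as to presence of disease and differences in Banff scores".

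Data Handling and Statistical Analysis names one test: "Detection rates would be compared by using the McNemar test". The power statement in that section covers only a rise in detection from 17% to 37% with 40 patients. The protocol gives no agreement measure, acceptable discordance rate or margin, no expected number of CEUS-normal patients, and no method for ordinal Banff scores.

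**The concern.** The expectation is worded as an absence of significant discordance, so a p-value above 0.05 would count in its favour. That raises two problems.

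- **Absence of significance is not agreement.** A small subset, not covered by the power calculation, will often give p > 0.05 whatever the degree of agreement.
- **The only test on offer answers a different question.** McNemar asks whether disagreements lean one way. Ten pairs positive only at the first site and ten positive only at the second give p = 1.00, exactly as five and five do.

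At stake is the reassurance that a CEUS-normal kidney can be sampled anywhere. The Introduction says that transplant pathology is often patchy and that a random core may be a poor sample. Whether a normal CEUS marks an exception is therefore a fair question, but the stated criterion would tend to support that answer even if the cores disagreed often.

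**Working it through.** **1. The plan's own figure.** No figure is given for random-random pairs. The stated 80% power concerns targeted versus random cores. If the 10% false-negative rate is read as 10% of the 17% positives, then p01 = 0.10 × 0.17 = 0.017 and p10 = 0.017 + 0.20 = 0.217. With n = 40, two-sided McNemar power is 81.8% (mid-p), 83.1% (uncorrected), 76.4% (normal approximation) or 72.3% (exact). The 80% is thus roughly reproduced under some variants. It says nothing about the concordance expectation.

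**2. What McNemar responds to.** Let b and c be the numbers of pairs positive only at the first site and only at the second. The uncorrected statistic is (b − c)²/(b + c). The exact test refers min(b, c) to a binomial with b + c trials and probability 0.5. Exact two-sided p-values:

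| b : c | pairs disagreeing | p |
|---|---|---|
| 5 : 5 | 10 | 1.00 |
| 10 : 10 | 20 | 1.00 |
| 20 : 20 | 40 | 1.00 |
| 9 : 1 | 10 | 0.021 |
| 6 : 0 | 6 | 0.031 |

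Forty balanced disagreements give no signal; six one-sided ones do.

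**3. Largest possible discordance for rejection.** The plan says "we expect 17% of random biopsies to be positive for rejection". Assume that this rate applies to both cores of a CEUS-normal pair. Then P(discordant) = 0.17 + 0.17 − 2 × P(both positive), which is at most 0.34. At that limit no positive core is ever confirmed by its partner. If the two cores were independent, the value would be 2 × 0.17 × 0.83 = 28.2%.

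**4. Chance of a significant result under balanced disagreement.** Set p10 = p01 = D/2. Discordant pairs m follow Bin(n, D), and b given m follows Bin(m, 0.5). Sum over all outcomes with two-sided p ≤ 0.05. The number of pairs is not in the documents, so n is an assumption and is varied. At D = 34%:

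| n pairs (assumed) | uncorrected | exact |
|---|---|---|
| 10 | 4.0% | 0.2% |
| 20 | 4.6% | 1.6% |
| 30 | 4.3% | 2.3% |
| 40 | 4.5% | 2.6% |

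With 20 pairs and D = 20%, the values are 4.4% and 0.5%. With D = 80%, which is impossible for rejection at a 17% rate but conceivable for any Banff difference reduced to a directional yes/no, they are 5.0% and 3.0%. Quadrupling the disagreement hardly moves the uncorrected result.

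**5. Unbalanced disagreement.** With p10 = 0.4 and p01 = 0.1 (illustrative values), exact McNemar is significant 37% of the time at n = 20 and 74% at n = 40.

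**6. What an estimate would show.** Exact (Clopper-Pearson) two-sided 95% upper limits for the discordant proportion:

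| n pairs (assumed) | 0 discordant | 2 discordant |
|---|---|---|
| 10 | 30.8% | 55.6% |
| 20 | 16.8% | 31.7% |
| 30 | 11.6% | 22.1% |
| 40 | 8.8% | 16.9% |

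**The case against.** The strongest reply is that the protocol never says McNemar will be applied to random-random pairs. It is named for detection rates and powered for the gain from targeting. Pair-level differences in disease and Banff scores will be recorded, so a descriptive account of agreement remains possible. This stands: a reader might infer that the protocol chose McNemar for this purpose, and the text does not say so. It does not rescue the criterion, however. The expectation is phrased in terms of significance, and no other test is offered for it.

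A reader might also infer that McNemar would stay non-significant however often the cores disagree. The documents do not support that. The first core usually comes from the upper pole and the second from elsewhere, so a systematic site difference is possible, and step 5 shows that the test could then reject. Such a result would point to site bias and would still not measure the amount of discordance.

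Finally, this is a self-described pilot, and the expectation is the last one listed. The title, the aim and the only power calculation concern targeting, and that comparison is untouched. No sentence commits the authors to report a CEUS-normal kidney as histologically uniform on the strength of p > 0.05, so a claim that the trial's main message is at risk would go too far. These points limit the severity. They also favour estimation, which suits a pilot better than a significance criterion.

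**Conclusion.** The concern holds in a limited form. The criterion is wrong as written, because failing to find significant discordance does not show concordance, and the only named test would not measure discordance if it were used. Under balanced disagreement it would be significant about 5% of the time or less: 4.6% uncorrected and 1.6% exact for an assumed 20 pairs at the 34% maximum for rejection.

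This rests on three assumptions: neither site is systematically worse, the 17% rate applies to both cores in CEUS-normal patients, and the number of pairs lies somewhere between 10 and 40. The result is insensitive to the last of these. It should be fixed, but it does not threaten the targeted-versus-random comparison.

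**What to change.** For CEUS-normal patients, replace the significance criterion with the proportion of discordant pairs and its exact 95% confidence interval, once for disease (yes/no) and once for any difference in Banff score. State that p > 0.05 will not be taken as evidence of concordance.

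In the same pairs, report detection at the accessible site minus detection at the second site. This shows whether site alone could contribute to a targeted-random difference.

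Comparing discordance between random-random and targeted-random pairs by Fisher's exact test is optional. It has low power: the plan's figures imply 0.217 + 0.017 = 23.4% discordance in targeted-random pairs, and with an assumed 20 pairs in each group power is about 25% against 5% discordance and 52% against 0%. A non-significant result there must not be read as similarity.

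The cost is revised wording in the hypothesis and statistical sections and one extra table. No additional patients, cores or data are needed. The downside is a wide interval, and hence a less decisive statement about concordance.

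### Nothing protects the CEUS-independent rule for the random core from an operator who has seen the CEUS; steering that core would exaggerate the targeted-versus-random difference

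*Combined protocol and SAP*

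**What the plan says.** All of the relevant procedure is in the Proposed investigation section.

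- Timing: "CEUS will be performed in addition to our routine color-Doppler ultrasound evaluation of the transplant kidney prior to the biopsy".
- Random core: "One core will be obtained from the most easily accessible location, usually the upper pole, without consideration of CEUS results".
- Targeted core: "A second core biopsy will be obtained from a segment that demonstrates variable CEUS perfusion". The same paragraph adds that low perfusion is what will be targeted and that areas with no perfusion will not be.
- Kidneys without a target: "If no abnormality is detected with CEUS, a second biopsy will still be performed in a distinctly separate location from the first".
- Sequence: "The order in which the randomized and targeted biopsies are performed will be randomized".
- Blinding: specimens are "labeled in order only as #1 and #2, blinded to the pathologists", while the full description of each core is "recorded by the performing radiologist prospectively".
- Site data: "The perfusion characteristics of each site based on CEUS findings will be recorded".

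The Data Handling and Statistical Analysis section compares detection rates by the McNemar test. It expects 17% of random cores to be positive and claims 80% power with 40 patients for a rise to 37%.

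**The concern.** The random core stands in for routine practice; the Hypothesis/Expected Results section makes a routine, non-targeted biopsy the comparator. Its value depends on its site being the one that would have been used had CEUS not been done. The plan asks for this but provides no means of securing it. The site is not marked before contrast, and it is not chosen by someone who has not seen the CEUS. Nor is there a rule for the case where the accessible site falls inside the segment to be targeted.

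That case matters most, because in those kidneys targeting adds least over routine practice. An operator who moves the random core so that the two samples differ turns two similar sites into a contrast and adds discordant pairs in favour of CEUS. The Expected Deliverables section says that the results may lead to a larger study, so an inflated estimate could carry into its planning.

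**Working it through.** **Does the operator know the CEUS result when placing the random core?** The documents do not say so in one sentence, but the provisions together imply it. CEUS comes before any core. The targeted core cannot be placed without it. Core order is randomised, so in targeted-first patients the CEUS finding has already been acted on when the random core is taken. The performing radiologist records which core is which. Only the pathologists are described as blinded.

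**The plan's own figures.** The printed formula gives 0.25 × 0.16 + 0.16 × 0.84 = 0.1744, stated as 17%. (The sentence before it names 12% for surveillance biopsies, which would give 0.1408; I use the stated 17%.)

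For power, let p10 be the probability of a positive targeted and negative random core, and p01 the reverse. Read the 10% false negative rate as p01 = 0.10 × 0.17 = 0.017, so p10 = 0.217. With d = p10 − p01 = 0.20 and s = p10 + p01 = 0.234:

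power = Φ[(d√40 − 1.96√s) / √(s − d²)] = Φ[(1.265 − 0.948) / 0.440] = 76.4%, two-sided.

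Enumerating the discordant pairs gives 72.3% (two-sided exact), 83.1% (two-sided uncorrected) and 82.0% (one-sided exact). The stated 80% lies within this spread and is not in dispute here.

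**Size of the inflation.** Inputs:

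- T = 0.37, positivity in low-perfusion tissue (the plan's target rate).
- R = 0.17, positivity at the unsteered accessible site (the plan's random rate).
- o, the share of kidneys whose accessible site lies in the low-perfusion segment (assumed).
- k, the share of those in which the random core is moved away (assumed).
- Every kidney has a target (assumed).

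The rate x in other cortex solves o·T + (1 − o)·x = R, so x = (R − o·T)/(1 − o). Inflation = k·o·(T − x).

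| o | x | Inflation, k = 1 | Observed difference, k = 1 (true 20) | Inflation, k = 0.5 |
|---|---|---|---|---|
| 20% | (0.17 − 0.074)/0.80 = 12.0% | 5.0 points | 25.0 points | 2.5 points |
| 25% | (0.17 − 0.0925)/0.75 = 10.3% | 6.7 points | 26.7 points | 3.3 points |
| 33% | (0.17 − 0.1233)/0.667 = 7.0% | 10.0 points | 30.0 points | 5.0 points |

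If T = x, the inflation is zero whatever o and k are.

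**A different anchor.** Suppose instead that 17% is the rate outside the low-perfusion segment. With full avoidance the observed difference is 20 points. The unsteered random rate would be 19%, 22% or 27% at overlap of 10%, 25% or 50%, so the true difference is 18, 15 or 10 points and the inflation 2, 5 or 10 (1, 2.5 or 5 at half avoidance). By the formula above, with p01 one tenth of the random rate, power for the true difference would be about 70%, 58% or 36%. Steering would make a smaller real effect look like the planned one.

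**What excluding overlapping pairs would do.** Dropping them leaves only random cores in other cortex, with rate x = 12.0%, 10.3% or 7.0% against 37%. That is the same 25.0, 26.7 or 30.0 points as full avoidance.

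**The case against.** A reader might infer that the random site is left to the operator's discretion. The documents do not support that. They give a rule, a usual location and an instruction to disregard CEUS, and moving the core because of CEUS would breach the instruction. What is missing is enforcement.

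The motive for steering is also conjecture. The plan asks for separate sites only when CEUS shows no abnormality, where both cores are random and there is no targeting contrast to inflate. No text asks for separation in targeted kidneys, so steering may be rare. This stands: confidence is high that the safeguard is absent, and much lower about the amount of bias.

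The recording of each site's perfusion is a real partial check. It would show whether random cores ever fall in low-perfusion tissue. It cannot show where a core would have gone without CEUS, so steering could not be reconstructed from it. Randomised order balances sequence effects and blinded pathology protects the reading; neither protects the choice of site.

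The bias could also run the other way. The plan says that non-perfused areas would not contribute to the diagnosis. Moving the random core off such an area could raise its detection rate. Fixing the site beforehand guards against both directions.

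**Conclusion.** The gap is real and worth closing, even in a pilot. The comparator's site rule relies on an operator who has seen the CEUS, and the handling of coinciding sites is unstated.

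Under the assumptions shown, the inflation is at most 5, 7 or 10 points with full avoidance and half that with 50% avoidance. These are ceilings in two respects: they assume complete avoidance and a target in every kidney. The documents give neither the overlap nor the avoidance rate, so the actual size is unknown.

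A reader might go further and infer that steering could produce a CEUS advantage with no real gain behind it. The documents do not support that as the general case. Steering needs disease to differ between low-perfusion and other cortex, so it normally enlarges a real difference. In the table the true gain is 20 points, and the false part is 20%, 25% or 33% of the observed 25.0, 26.7 or 30.0. Only in a kidney whose accessible site already lies in the low-perfusion segment would the whole contrast be produced by steering. Kidneys with no CEUS abnormality are not affected.

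**What to change.** 1. Choose the random site on the routine color-Doppler scan and save it on an annotated image before Optison is given.
2. State in the protocol how the random core is handled when CEUS later shows that the recorded site lies in the low-perfusion segment. By default the recorded site stands.
3. Add form fields for any departure from the recorded site, with its reason, and for any overlap with the low-perfusion segment.
4. Keep overlapping pairs in the primary McNemar analysis, classified by the pre-recorded site. Report the number of overlaps and departures.
5. Do not use exclusion of overlapping pairs as a robustness check, since it recreates the bias.

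The cost is one saved image and a short form entry per patient. The routine scan and the REDCap forms are already planned. The downside is that some pairs will come from the same region, so the apparent effect may be smaller; that is the comparison with routine practice that the study sets out to make.

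### The stated 80% power holds only if essentially all 40 patients give a targeted-versus-random pair, which the design does not guarantee

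*Combined protocol and SAP*

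**What the plan says.** - **Test and power** (Data Handling and Statistical Analysis): "Detection rates would be compared by using the McNemar test", and "a sample of 40 patients has 80% power (alpha .05) if detection increases by 20 percentage points from 17% to 37" per cent. The lower rate belongs to random cores: "we expect 17% of random biopsies to be positive for rejection". The calculation is qualified by "assuming a 10% false negative rate by CEUS biopsy". Neither the sidedness of alpha nor the version of McNemar is given.
- **Enrolment** (Proposed investigation): "this pilot study of 40 consecutive consenting male and female adult patients over 18 years of age". An abnormal CEUS is not an entry condition.
- **Cores** (Proposed investigation): one core is taken without regard to CEUS and labelled random. For the other, "A second core biopsy will be obtained from a segment that demonstrates variable CEUS perfusion", and it is labelled targeted. Without such a segment, "If no abnormality is detected with CEUS, a second biopsy will still be performed in a distinctly separate location from the first", and that core is also labelled random.
- **Hypotheses** (Hypothesis/Expected Results): targeted cores are expected to show disease more often, or at higher severity, than random ones. Patients with a normal CEUS have a hypothesis of their own, namely that untargeted cores "of different segments in the same kidney, when no focal or segmental CEUS abnormality is demonstrated, will not be significantly discordant for disease or Banff".

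The protocol does not state what share of patients should have an abnormal CEUS, does not enlarge the 40 to allow for the others, and does not say how the McNemar test treats a patient with two random cores.

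**The concern.** McNemar's test of targeted against random detection needs one result of each kind per patient. A patient with a normal CEUS supplies two random results. The plan foresees such patients and expects no material difference between their cores, yet the power sentence counts every enrolled patient towards a 20-point difference.

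Two things are at stake. If only targeted pairs are analysed, there are fewer than 40 of them and power is lower than stated. If all 40 stay in the test, the normal-CEUS patients add pairs with no expected difference and dilute the effect. Because the analysis set is not defined, that choice could also be made after the results are known. In either case a null result would be set against a power claim that may not apply to it.

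**Working it through.** **Inputs.** From Data Handling and Statistical Analysis: n = 40, random-core detection 17%, targeted-core detection 37%, alpha 0.05, 10% false negatives. The protocol's 17% is taken as given. Assumptions made here:
- The test is two-sided.
- The 10% is the share of random-positive patients whose targeted core is negative.
- The share *f* of patients with an abnormal CEUS is unknown and is varied.

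**Discordant cells.**
- Targeted negative, random positive: 0.10 × 0.17 = 0.017.
- Targeted positive, random negative: 0.017 + 0.20 = 0.217.
- Total discordance p_d = 0.234; difference d = 0.20.

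**Methods.** For the exact, mid-p and uncorrected chi-square versions, the number of discordant pairs is M ~ Binomial(n, 0.234). Given M, the number favouring the targeted core is Binomial(M, 0.217/0.234). Power is the summed probability of all significant outcomes. The usual formula is

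Power = Φ[(d√n − 1.96√p_d) / √(p_d − d²)].

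**Reproducing the plan's figure (40 pairs).** Formula: (0.20 × 6.325 − 1.96 × 0.4837) / √0.194 = 0.317 / 0.440 = 0.72, so power is 76%. Enumeration gives 72% exact, 82% mid-p and 83% uncorrected. The stated 80% is thus reproduced to within about 2 points by mid-p, with all 40 patients as informative pairs. If the 10% is instead taken as a share of the 37% (cells 0.037 and 0.237), a one-sided version of the formula gives 79.8%, again with 40 pairs.

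**Targeted pairs only, same 20-point rise.**

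| Targeted pairs (f) | Exact | Mid-p | Formula | Uncorrected |
|---|---|---|---|---|
| 40 (100%) | 72% | 82% | 76% | 83% |
| 30 (75%) | 50% | 65% | 63% | 71% |
| 20 (50%) | 20% | 35% | 45% | 50% |
| 10 (25%) | 1% | 4% | 24% | 14% |

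The expected number of discordant pairs explains the fall: 0.234 × n is 9.4, 7.0, 4.7 and 2.3. Even if every discordant pair favours the targeted core, two-sided significance needs at least 6 (exact), 5 (mid-p) or 4 (uncorrected).

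**Where 80% is lost.** Mid-p gives 80.5% at 39 pairs and 79.2% at 38. Uncorrected gives 80.0% at 37 and 78.8% at 36. So about two to four normal-CEUS patients are enough. The exact test and the formula do not reach 80% even at 40 pairs.

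**All 40 kept in the test.** Let random/random pairs be discordant with probability c in each direction (c is an assumption, 1.7% to 10%). The cells become 0.017f + c(1 − f) and 0.217f + c(1 − f), and the overall difference is 20f points. At f = 75% that is 15 points, with cells 0.017/0.167 for c = 1.7% and 0.038/0.188 for c = 10%.

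| f | Exact | Mid-p | Uncorrected |
|---|---|---|---|
| 75% | 40–48% | 51–62% | 52–66% |
| 50% | 16–20% | 24–33% | 25–43% |

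**If the 20 points is an average over all 40.** The 40-pair power then stands unchanged. The rise needed in targeted patients is 20/f: 20/0.75 = 27 points, or 20/0.50 = 40 points.

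**The case against.** **The loss is conditional on a share that nobody has stated.** This stands. If 39 of 40 patients have a target, mid-p power is still 80.5%. The targeting criterion is broad (variable, decreased or inhomogeneous perfusion), and the Introduction argues that transplant pathology is often patchy. A reader might infer from the 84% surveillance case mix that few patients will be targetable. The documents do not support that: they describe those patients as lacking other evidence of renal dysfunction, which says nothing direct about segmental perfusion.

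**Part of any shortfall is choice of test.** This also stands. Exact power is 72% with no normal-CEUS patient at all, so the loss has to be read within one version. At 30 pairs it is 72 to 50 (exact), 82 to 65 (mid-p), 76 to 63 (formula) or 83 to 71 (uncorrected).

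**The 20 points may be a whole-cohort figure.** The 17% is built from the unselected case mix, so this reading is possible, and power would then hold. But the protocol does not say so, its main hypothesis compares targeted with random cores, and it gives normal-CEUS patients a separate one. A rise of 27 or 40 points in targeted patients is stated nowhere.

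**The labels already keep the groups apart.** Largely true. The second core of a normal-CEUS patient is prospectively recorded as random, and nothing suggests that it will be counted as targeted. What is missing is an explicit analysis set.

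**It is a pilot.** True, and this tempers the consequences. The protocol nevertheless attaches 80% power to a significance test and foresees publication and possibly a larger study, so the figure should match the design.

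**Conclusion.** The point stands in conditional form. The 80% rests on 40 informative pairs; the design does not secure them, and the plan gives no abnormal-CEUS share from which the real number could be worked out. Under the versions that reach 80% at all, about two to four normal-CEUS patients take power below it. At an assumed 75% share power is 50–71%, and at 50% it is 20–50%, depending on the version of McNemar.

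A reader might go further and conclude that the trial is underpowered, or that its real power is half the stated figure or less. The documents do not support that. It would need a share of roughly 50% or lower under most versions, and no share is given. What can be said is that the power sentence is wrong as an unqualified statement and that the primary analysis set is undefined.

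The figures assume a two-sided 5% test, cells of 1.7% and 21.7%, and that the whole-cohort 17% and the 20-point rise carry over to patients with an abnormal CEUS.

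**What to change.** In Data Handling and Statistical Analysis:

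1. Define the primary McNemar set as patients with both a targeted and a random core, and state that a second random core is never counted as targeted.
2. Replace the power sentence with power, or the detectable rise, for 40, 30, 20 and 10 targeted pairs. Name the McNemar version, the sidedness and the discordance assumed, and give the expected abnormal-CEUS share if the investigators have a basis for one.
3. Use random/random pairs only for the normal-CEUS hypothesis.
4. Report any comparison over all 40 patients as secondary, and label it as diluted.

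This needs no extra patients and fits the forty contrast vials requested. The cost is wording and a less favourable stated power. It makes the claim honest but recovers no power: reaching 40 targeted pairs would take 40/0.75 ≈ 54 enrolled at a 75% share, or 40/0.50 = 80 at 50%.
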